#### **7.3.8.1 Swollen/Tender Joint Counts**

All joint assessments will be performed by an experienced assessor who has been trained by viewing Amgen's Group for Research and Assessment of Psoriasis and Psoriatic Arthritis (GRAPPA) training module and must be identified on the delegation of authority for this responsibility. The user ID of the joint assessor will be recorded at each assessment. The score for each joint will be recorded directly into the electronic PRO tablet which will serve as the source documentation and will not be transposed to the eCRF. Joints that have been replaced are considered inevaluable.

*Swollen Joint Count Assessments* – A total of 66 joints will be scored for presence or absence of swelling.

*Tender Joint Count Assessments* – A total of 68 joints will be scored for presence or absence of tenderness.

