10.6.5 Exposure to Concomitant Medication

A summary of all concomitant medications reported may be provided by preferred term as coded by the World Health Organization Drug (WHODRUG) dictionary.

11. Changes From Protocol-specified Analyses

Changes are made only for secondary or exploratory endpoints. The changes are instituted to adopt the standardized ways to report the efficacy endpoints in PsA trials.

The changes to LDI, SPARCC, and mNAPSI are made to focus on relevant sub-populations for analysis. Modeling analyses described in [Section 10.5.2](#) will be

limited to selected secondary endpoints at week 24 only, for the inclusion in CSR.
Further analyses may be performed later on an ad hoc basis.

Specifically, the changes are as follows:

1. These analysis sets are added to the SAP because they are more relevant to the purpose of the analyses focusing on the subpopulations with disease progression.

Leeds Dactylitis Index (LDI) Analysis Set

The leeds dactylitis index analysis set will consist of all the randomized subjects with non-zero LDI at baseline. Subjects will be analyzed according to their randomized treatment group. Analyses of LDI efficacy endpoints will be based on the leeds dactylitis index analysis set.

Modified Nail Psoriasis Severity Index (mNAPSI) Analysis Set

The mNAPSI analysis set will consist of all the randomized subjects with non-zero mNAPSI at baseline. Subjects will be analyzed according to their randomized treatment group. Analyses of mNAPSI efficacy endpoints will be based on this analysis set.

SPARCC Enthesitis Analysis Set

The SPARCC Enthesitis Analysis Set will consist of the randomized subjects with non-zero SPARCC enthesitis at baseline. Subjects will be analyzed according to their randomized treatment group. Analyses of SPARCC efficacy endpoints will be based on the SPARCC Enthesitis analysis set.

2. Modification of the other secondary endpoints limited to specific subpopulation in in [Section 4.1.3](#) as follows:

For subjects with non-zero mNAPSI at baseline,

- mNAPSI and change from baseline at week 24
- achievement of mNAPSI = 0 at week 24

For subjects with non-zero Leeds Dactylitis Index (LDI) at baseline,

- LDI and change from baseline at week 24
- achievement of LDI = 0 at week 24

For subjects with non-zero Spondyloarthritis Research Consortium of Canada (SPARCC) enthesitis at baseline,

- SPARCC enthesitis score and change from baseline at week 24
- achievement of SPARCC score = 0 at week 24

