| Week 12 | 85 | Study Day 2 to 126 | 124 |
| Week 24 | 169 | Study Day 127 to 210 | 84 |
| Week 36 | 253 | Study Day 211 to 294 | 84 |
| Week 48 | 337 | >=Study Day 295 | n/a |

For the rest of the endpoints of interest, use the following window:

| Visit Week | Target Day | Window Definition | Interval (days) |
|-----------------------|------------|--|-----------------|
| Baseline ^a | 1 | Last Evaluation prior to or on Study Day 1 | n/a |
| Week 4 | 29 | Study Day 2 to 42 | 41 |
| Week 8 | 57 | Study Day 43 to 70 | 28 |
| Week 12 | 85 | Study Day 71 to 98 | 28 |
| Week 16 | 113 | Study Day 99 to 140 | 42 |
| Week 24 | 169 | Study Day 141 to 210 | 70 |
| Week 36 | 253 | Study Day 211 to 294 | 84 |
| Week 48 | 337 | >=Study Day 295 | n/a |

^a For swollen joint count and tender joint count, the baseline values are the values taken on the day of randomization before the first dose of investigational product.

Scoring Algorithms for Efficacy Endpoints

ACR Responder

The ACR response is a composite endpoint that classifies a patient as a responder or non-responder based upon improvement from baseline as defined by 7 endpoints. To be considered an ACR 20/50/70 responder, a subject must experience the following:

- At least 20/50/70% improvement in tender joint count (68 joints), AND
- At least 20/50/70% improvement in swollen joint count (66 joints), AND
- At least 20/50/70% improvement in 3 of the 5 following endpoints:
 - Physician global assessment (PhGA)
 - Patient global assessment (PtGA)
 - Patient global assessment of joint pain
 - Functional disability (HAQ-DI)
 - Acute phase reactant (CRP)

If joint data are partially missing, the joint counts will be prorated prior to deriving ACR responses. There is no imputation for missing secondary individual components (ie, HAQ-DI, CRP or ESR, pain VAS, PtGA, and PhGA).

In the case that some ACR components are missing, the ACR scores will be based on the non-missing components. If a subject's non-missing components are not sufficient to determine ACR response, then that subject will be considered as missing ACR response. The corresponding algorithm is listed below (using ACR 20 as an example):

1. If either swollen or tender joint counts is not improved at least 20%, the subject is an ACR non-responder
2. If both tender and swollen joint counts are improved at least 20%, and
 - a. If 3 or more of the other 5 ACR components are improved at least 20%, the subject is an ACR 20 responder;

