The HAQ-DI is the disability assessment component of the HAQ that assesses a patient's level of functional ability. It is calculated based on the mean score from the following eight categories: dressing & grooming, rising, eating, walking, hygiene, reach, grip, and usual activities. Each category is comprised of two or three questions that are scored as 0 (without any difficulty), 1 (with some difficulty), 2 (with much difficulty), or 3 (unable to do). The highest score for questions in each category (range 0 to 3)

determines the score for the category, unless aids or devices are required. Dependence on equipment or physical assistance increases a lower score (ie, scores of 0 or 1) to the level of 2 to more accurately represent underlying disability. If the subject's highest score is a 3 then it stays a 3. Devices and aids are assigned to the categories as follows:

| HAQ-DI Category | Companion AIDS OR DEVICES item |
|---------------------|--|
| DRESSING & GROOMING | Devices used for dressing (button hook, zipper pull, long-handled shoe horn, etc.) |
| ARISING | Built up or special chair |
| EATING | Built up or special utensils |
| WALKING | Cane, walker, crutches, wheelchair |
| HYGIENE | Raised toilet seat, bathtub seat, bathtub bar, long-handled appliances in bathroom |
| REACH | Long-handled appliances for reach |
| GRIP | Jar opener (for jars previously opened) |

The eight category scores are averaged into an overall HAQ-DI score on a scale from 0 (no disability) to 3 (completely disabled) when 6 or more categories are non-missing. If more than 2 categories are missing, the HAQ-DI score is set to missing.

Minimal Disease Activity (MDA)

MDA response will be derived based on the following criteria:

| Outcome | Criteria |
|---|----------|
| Tender joint count (0-68) | ≤ 1 |
| Swollen joint count (0-66) | ≤ 1 |
| Body surface area (0-100) | ≤ 3 |
| Patient global assessment of joint pain – PTGAJP (0-100) (used for patient pain VAS) | ≤ 15 |
| Patient global assessment of disease activity – PTGA (0-100) (used for patient global disease activity VAS) | ≤ 20 |
| HAQ-DI (0-3) (used for HAQ) | ≤ 0.5 |
| SPARCC enthesitis index (0-16) (used for tender enthesesal points) | ≤ 1 |

Use prorated scores for Tender and Swollen joint count. If 5 of 7 criteria are met then the subject has achieved MDA response.

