If all components are missing, then MDA is set to be missing. If one or more but not all components are missing in the formula, then MDA is set to be zero.

Very Low Disease Activity (VLDA)

VLDA response will be derived based on the following criteria:

| Outcome | Criteria |
|--|----------|
| Tender joint count (0-68) | ≤ 1 |
| Swollen joint count (0-66) | ≤ 1 |
| Body surface area (0-100) | ≤ 3 |
| Patient global assessment of joint pain (0-100) (used for patient pain VAS) | ≤ 15 |
| Patient global assessment of disease activity (0-100) (used for patient global disease activity VAS) | ≤ 20 |
| HAQ-DI (0-3) (used for HAQ) | ≤ 0.5 |
| SPARCC enthesitis index (0-16) (used for tender enthesial points) | ≤ 1 |

Use prorated scores for Tender and Swollen joint count. If all 7 criteria are met then the subject has achieved VLDA response. If all components are missing, then VLDA is set to be missing. If one or more but not all components are missing in the formula, then VLDA is set to be zero.

mNAPSI

The modified NAPSI will be calculated for all fingernails at baseline. For remaining visits, the modified NAPSI will only be calculated for the worst fingernail (ie, the fingernail with the highest score) based on the baseline assessment. The total score will range from 0-13 as follows:

| Clinical feature | Score |
|--|------------------|
| Pitting (0-3 based on severity)* | 0, 1, 2 or 3 |
| Nail plate crumbling (0-3 based on severity)* | 0, 1, 2 or 3 |
| Onycholysis and oil drop dyschromia (0-3 based on severity)* | 0, 1, 2 or 3 |
| Leukonychia (0=absent, 1=present) | 0 or 1 |
| Red spots in lunula (0=absent, 1=present) | 0 or 1 |
| Nail bed hyperkeratosis (0=absent, 1=present) | 0 or 1 |
| Splinter hemorrhages (0=absent, 1=present) | 0 or 1 |
| Total mNAPSI Score | sum (range 0-13) |

| Severity Codes | | | | |
|-------------------------------------|----------------|---------|---------|---------|
| Clinical feature | Score=0 | Score=1 | Score=2 | Score=3 |
| Pitting | no pits | 1-10 | 11-49 | ≥50 |
| Nail plate crumbling | no crumbling | 1-25% | 26-50% | >50% |
| Onycholysis and oil drop dyschromia | no onycholysis | 1-10% | 11-30% | >30% |

If one or more components are missing, then mNAPSI is set to be missing.

PASDAS

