- Use the non-missing score from the reader if the score from the other reader is missing, and adjudicator scores are unavailable
- Set to missing if both scores from 2 readers are missing and no adjudicator scores are available

Swollen Joint Count

The swollen joint count is an assessment of the swelling of joints using 0-1 point scale (0 = none, 1 = present). The total swollen joint count is calculated by summing the number of joints with present swelling. If a joint has been replaced, fused, fractured or receives an intra-articular steroid injection, it will be counted as swollen at all visits subsequent to the replacement or injection.

| Swollen Joint Count (66) | |
|--|---|
| Temporomandibular joints (n=2) | Metacarpophalangeal joints (MCP) (n=10) |
| Sternoclavicular joints (n=2) | Fingers distal interphalangeal joints (DIP) (n=8) |
| Acromioclavicular joints (n=2) | Knees (n=2) |
| Shoulders (n=2) | Ankles (n=2) |
| Elbows (n=2) | Tarsi (n=2) |
| Wrists (n=2) | Metatarsal phalangeal joints (MTP) (n=10) |
| Fingers proximal interphalangeal joints (PIP) (n=10) | Toes proximal interphalangeal joints (PIP) (n=10) |

| Swollen Joint Count (28) | |
|---------------------------------|--|
| Shoulders (n=2) | Metacarpophalangeal joints (MCP) (n=10) |
| Elbows (n=2) | Proximal interphalangeal joints (Fingers PIP) (n=10) |
| Wrists (n=2) | Knees (n=2) |

If at least half but not all joints are evaluable (33 for the 66 joint count or 14 for the 28 joint count), then the prorated swollen joint count will be calculated. The prorated score will be adjusted based upon the number of evaluable joints: the counted score will be multiplied by 66 or 28 as applicable and divided by the number of joints evaluated. Otherwise, the number of swollen joints is missing.

Tender Joint Count

The tender joint count is an assessment of the pain and/or tenderness of joints using 0-1 point scale (0 = none, 1 = present). The total tender joint count is calculated by summing the number of joints with present tenderness. If a joint has been replaced, fused, fractured or receives an intra-articular steroid injection, it will be counted as tender at all visits subsequent to the replacement or injection.

| Tender Joint Count (68) | |
|--|---|
| Temporomandibular joints (n=2) | Metacarpophalangeal joints (MCP) (n=10) |
| Sternoclavicular joints (n=2) | Metatarsal phalangeal joints (MTP) (n=10) |
| Acromioclavicular joints (n=2) | Toes proximal interphalangeal joints (PIP) (n=10) |

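### SAP Appendix A scores replaced joints as swollen and tender where the protocol makes them inevaluable; read literally, pre-study prostheses then count as active disease in ACR 20 and MDA

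*SAP*

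**What the plan says.** Protocol 7.3.8.1, on the swollen and tender joint assessments, states: "Joints that have been replaced are considered inevaluable". It sets no time limit and covers both the 66-joint and the 68-joint count.

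SAP Appendix A gives a different rule. For the swollen count, the rule for affected joints reads: "replaced, fused, fractured or receives an intra-articular steroid injection, it will be counted as swollen at all visits subsequent to the replacement or injection". For the tender count, the parallel sentence ends: "it will be counted as tender at all visits subsequent to the replacement or injection".

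The same appendix has a general rule for joints that are not evaluated. If at least half can be evaluated, "the counted score will be multiplied by 66 or 28 as applicable and divided by the number of joints evaluated", with 68 in place of 66 for the tender count. This feeds both multiplicity-controlled endpoints. For ACR 20, "If joint data are partially missing, the joint counts will be prorated prior to deriving ACR responses". For MDA and VLDA, "Use prorated scores for Tender and Swollen joint count".

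ACR 20 requires at least 20% improvement in both counts. MDA requires five of seven criteria, two of which are a tender count and a swollen count of at most 1. For VLDA, "If all 7 criteria are met then the subject has achieved VLDA response".

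SAP section 11 introduces its list of departures from the protocol with: "Changes are made only for secondary or exploratory endpoints". The list does not mention joint scoring.

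**The concern.** A joint cannot be both inevaluable and scored as active. The two treatments give different counts, and the counts decide ACR 20 and contribute to MDA.

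Pre-study prostheses matter most. The baseline visit and every later visit come after such a replacement, so the SAP wording, taken at face value, scores the prosthesis as swollen and tender throughout. No treatment can clear it. Eligibility does not remove these subjects: exclusion criterion 204 concerns recent joint infection, not the presence of a prosthesis. Low joint counts, where one extra joint weighs most, are also eligible, because inclusion criterion 104 asks for only 3 tender and 3 swollen joints.

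The stake is the responder status of individual subjects on the primary and key secondary endpoints.

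**Working it through.** No figure in the plan is in dispute, so the check compares the two rules on the same subject. All counts below are assumed examples, because the documents give no frequency of replaced joints.

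**Notation.** N = 66 or 68; k = replaced joints; b and w = active native joints at baseline and week 24. Unless stated, all other joints are evaluated.

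- SAP count: native active + k
- Inevaluable and prorated: native active × N/(N − k)

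**1. Joints replaced before baseline (literal reading).** Improvement is (b − w)/(b + k) under the SAP rule. Under proration the factor N/(N − k) cancels, leaving (b − w)/b. Whenever w is below b, the SAP figure is smaller.

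| Native joints | k | Prorated | SAP rule |
|---|---|---|---|
| 5 to 4 | 1 | 5.08 to 4.06, 20.0% (meets 20%) | 6 to 5, 16.7% (fails) |
| 10 to 8 | 1 | 10.15 to 8.12, 20.0% (meets) | 11 to 9, 18.2% (fails) |
| 4 to 3 | 2 | 4.13 to 3.09, 25.0% (meets) | 6 to 5, 16.7% (fails) |
| 3 to 2 | 1 | 3.05 to 2.03, 33.3% (meets) | 4 to 3, 25.0% (meets) |

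The counts shown are for N = 66; N = 68 gives the same percentages.

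The number of joints that must clear rises from ceil(b/5) to ceil((b + k)/5). For b = 3 to 30 it changes at 6 of 28 values with k = 1 (b = 5, 10, 15, 20, 25, 30) and at 12 of 28 with k = 2. These are tallies of possible baseline values, not proportions of subjects.

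**2. One joint replaced after baseline (on-study reading).** Here w excludes the replaced joint, and the baseline count is b.

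- b = 3, w = 2: SAP count 3, improvement 0%; prorated 2 × 66/65 = 2.03, improvement 32.3%.
- b = 6, w = 4: SAP count 5, 16.7%; prorated 4.06, 32.3%.
- b = 5, w = 3: SAP count 4, 20.0%; prorated 3.05, 39.1%. Both pass.

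The largest w that still passes differs by one joint at 19 of the 28 baseline values, in both counts. Again these are values, not subjects; status changes only for a subject at exactly that w who otherwise qualifies.

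**3. MDA and VLDA.** Two replaced joints that are in both counts (for example both knees), with no active native joint, give 2 under the SAP rule and 0 under proration. The SAP count cannot fall below 2, so both joint criteria fail at every visit after the replacements. MDA then needs all five other criteria, and VLDA cannot be reached. Hips are in the 68-joint list only, so a replaced hip affects only the tender count.

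One replaced joint with no active native joint gives 1 versus 0, and both pass. If one further joint is unevaluated, the SAP count becomes 66/65 = 1.015, which exceeds 1, while the prorated count stays 0.

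**4. Direction.** For replacement after baseline, the SAP count minus the prorated count is k(N − k − w)/(N − k). This is never negative, so the SAP rule is never the more lenient. For replacement before baseline the direction is usual but not universal, because heavy missingness at baseline can reverse it. Take k = 1, 20 other joints missing at baseline with 6 active, then 7 active and none missing at week 24:

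- SAP: baseline 7 × 66/46 = 10.04, week 24 = 8, improvement 20.3% (passes).
- Prorated: baseline 6 × 66/45 = 8.80, week 24 = 7 × 66/65 = 7.11, improvement 19.2% (fails).

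**The case against.** **The protocol sentence is an assessment rule.** It stands beside assessor training and tablet entry; Protocol section 10 has no rule for inevaluable joints and leaves statistical detail to the SAP. A reader might infer that section 11 conceals a change to the primary analysis. The documents do not support that: it is arguable that no protocol-specified analysis was altered. The section 11 point is therefore secondary. What stands is that a joint recorded as inevaluable under the protocol is scored as active by the SAP, and nothing links the two.

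**The SAP names replaced joints.** A reader might infer that Appendix A leaves precedence open between scoring as active and prorating. That overstates it, because on ordinary reading the specific rule overrides the general one. A sentence saying so is worth adding, but its absence is not the main fault.

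**For on-study replacement the SAP rule is a defensible conservative convention.** In the example with 3 joints at baseline and 2 still swollen, if the replaced joint was one of the three, proration would credit surgery as response. This stands, and the fix keeps the rule for that case.

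**The wording may mean on-study events only.** The present tense for injections and the reference to later visits fit that reading. If it is intended, pre-study prostheses raise no conflict and only a clarification is needed. The text does not say so.

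**It affects few subjects, equally in all arms.** This also stands. The tallies out of 28 might be read as frequencies, and the direction as invariable; neither reading is right. Failing both MDA joint criteria does not by itself rule out MDA.

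**Conclusion.** The point holds for replaced joints. The protocol makes them inevaluable and the SAP scores them as active. Read literally, the SAP rule carries pre-study prostheses into both mandatory ACR 20 counts and two of the seven MDA criteria as disease that cannot resolve. Individual subjects can change status: 16.7% against 20.0% with one prosthesis and native joints 5 to 4, and counts of 2 against 0 with two prostheses.

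This rests on the literal reading for joints replaced before baseline, and on proration as the consequence of being inevaluable, which is the SAP's own treatment. The rule is common to all arms and generally favours non-response, with exceptions when many other joints are missing at baseline.

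A reader might infer a bias between arms or a loss of power. The documents support neither, because they give no number of subjects with replaced joints; the trial-level effect is probably small and cannot be quantified. The protocol is silent on fused, fractured and injected joints, so there is no contradiction there. The SAP names a start point only for replacement and injection, so fused and fractured joints need a minor clarification. The point merits correction because it is a specific, cheap repair to the derivation of the primary and key secondary endpoints, not because a material effect has been shown.

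**What to change.** Before unblinding:

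1. In SAP Appendix A, state that joints replaced before the baseline assessment are inevaluable and handled by the existing proration, in line with Protocol 7.3.8.1.
2. Limit scoring as swollen or tender to events after baseline, and say that for those joints this rule applies instead of proration. As a minor addition, give a start point for fused and fractured joints.
3. In SAP section 11, note that scoring joints replaced on study as active differs from Protocol 7.3.8.1 and feeds ACR 20 and MDA.

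The cost is a few sentences in Appendix A and one entry in section 11. The data source should be confirmed, not assumed. The documents do not say whether the tablet records why a joint is inevaluable, and they name no source for replacement, fusion or fracture dates. Doing this before unblinding matters because a later choice between the two treatments would be made with knowledge of who becomes a responder.

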Appendix B. Code Fragments

CCI

CCI

CCI

Appendix C. Reference Values/Toxicity Grades

Adverse event severity is graded based on the National Cancer Institute Common Toxicity Criteria for Adverse Events (CTCAE) version 4.0.

Laboratory toxicity is graded based on the National Cancer Institute Common Toxicity Criteria (CTC) version 4.0 with the following additions:

| | Grade | | | | |
|-----------------|--|--------------------------------|---|--------------------------|------------|
| | 0 | 1 | 2 | 3 | 4 |
| BUN | WNL | >1.5 – 2.0 x ULN | >2.0 – 3.0 x ULN | >3.0 – 4.0 x ULN | >4.0 x ULN |
| HGB | WNL | >ULN | >(ULN+1) – (ULN+2) | >(ULN+2) | - |
| Urine Protein | NEG, NEGATIVE, TRACE, NORMAL, NOT DETECTED | +, +1, 1+ | ++, +2, 2+, +++, +3, 3+ | ++++, +4, 4+ | - |
| Platelet Count | WNL | > ULN – $1.0 \times 10^{12}/L$ | > $1.0 \times 10^{12}/L$ | - | - |
| Leukocyte Count | WNL | > ULN – $2.0 \times 10^{10}/L$ | > $2.0 \times 10^{10}/L$ – $4.0 \times 10^{10}/L$ | > $4.0 \times 10^{10}/L$ | - |
